#### **Study design**

To test whether the inhibition of  $\beta$ -endorphin ( $\mu$ -opioid) receptor alleviates itch in patients under chronic arsenic exposure, we conducted a randomized, double-blind, placebo-controlled trial. We randomly assigned patients to naloxone (0.4 mg/qd, sublingual) and placebo (0.4 mg/qd, sublingual) using a computer-generated sequence of random numbers during January 2019 to March 2019. The trial consisted of a one-week treatment period and a one-week withdrawal period. The primary outcome (severity of itch) was evaluated using the NRS through a face-to-face interview on baseline (Day 0) and the last day of the treatment period (Day 7), and a telephone interview on the last day of the withdrawal period (Day 14). The participants were also inquired about the possible adverse events of naloxone such as headache, sleep difficulty, sickness, and dizziness in each interview.

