#### **Statistical analysis**

In the randomized controlled trial, an intention-to-treat (ITT) analysis was performed to evaluate the efficacy of naloxone. The last observation carry-forward (LOCF) imputation method was used for unmeasured data in drop-out participants. Mixed effect models were used to estimate the efficacy, by constructing a model:  $Y = \beta_0 + \beta_1 \text{Group} + \beta_2 \text{Time} + \beta_3(\text{Group} \times \text{Time}) + e_i + v_{ij}$ , where  $\beta_3$  is the estimate for efficacy;  $e_i$  and  $v_{ij}$  refer to the errors between individuals and within an individual (repeated measurements), respectively. Statistical analyses were performed in R Statistical Software 3.4.1. The significance level for all statistical tests was 0.05.

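### Adverse-event questioning is framed around presumed naloxone effects, with no open question or all-cause recording described, so unexpected events may be under-recorded

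*Combined protocol and SAP*

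**What the plan says.** The Study design section gives safety one sentence, which says that participants were "inquired about the possible adverse events of naloxone such as headache, sleep difficulty, sickness, and dizziness in each interview". The interviews are those used for the itch score, held in person at Day 0 and Day 7 and by telephone at Day 14. Follow-up is short: "The trial consisted of a one-week treatment period and a one-week withdrawal period".

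The same section describes the design in these terms: "we conducted a randomized, double-blind, placebo-controlled trial". It describes no difference between the arms in how participants were questioned.

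The Statistical analysis section is about efficacy: "an intention-to-treat (ITT) analysis was performed to evaluate the efficacy of naloxone". It specifies no table, comparison or other summary of adverse events.

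Neither section describes an open question, a route for spontaneous reports, an adverse-event definition, severity grading, a seriousness criterion, or collection between interviews. Neither says that events raised by a participant were refused or left unrecorded.

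**The concern.** The scope of the questioning is set by presumed cause. An interviewer following the sentence as written asks about effects someone already thinks naloxone might have. Anything else depends on the participant raising it unprompted, at an interview a week after the previous one.

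This gives up an advantage of the design. With a concurrent blinded placebo arm, nobody needs to decide in advance which events belong to the drug. All events can be recorded and the arms compared. Filtering by presumed cause when the question is asked removes the events for which that comparison would be most informative.

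There is a second loss. Prompted symptoms are also asked about at Day 0, so they have a pre-treatment reference. An unprompted event has none, and is harder to interpret even when it is volunteered.

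At stake is how far an absence of unexpected events could be relied on. The primary itch outcome is not affected.

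**Working it through.** The plan gives no safety figure to reproduce. It states no sample size, adverse-event rate, allocation ratio or safety margin. The check is a reading of the text, followed by two illustrations on assumed inputs.

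**Reading.** The sentence has two layers. The category asked about is possible adverse effects of naloxone; the four symptoms illustrate that category. The list is therefore open, but only within presumed drug effects. Nothing else in the Study design or Statistical analysis section widens it to all health problems.

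**Direction of the effect.** Let p1 and p0 be the true proportions with an unexpected event on naloxone and on placebo. Let s be the share of such events that is recorded, assumed equal in the two arms.

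- Expected observed risk difference: s × p1 − s × p0 = s × (p1 − p0).
- Expected observed risk ratio: (s × p1) / (s × p0) = p1 / p0.

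| s (assumed) | Observed difference as a share of the true one | Risk ratio |
|---|---|---|
| 1.0 | 100% | unchanged |
| 0.8 | 80% | unchanged |
| 0.5 | 50% | unchanged |
| 0.3 | 30% | unchanged |

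Equal under-capture shrinks absolute rates and differences and lowers precision. It does not by itself distort the ratio between arms.

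**Chance of recording the event at all.** Three inputs are assumed: n participants on naloxone, an event outside the prompted category in 5% of them, and a share v of affected participants whose event is recorded (v = 1 means every event is elicited). With independent participants, the chance of at least one recorded event is 1 − (1 − 0.05 × v)^n.

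| v | Calculation, n = 60 | Result | Calculation, n = 30 | Result |
|---|---|---|---|---|
| 1 | 1 − 0.95^60 | 0.954 | 1 − 0.95^30 | 0.785 |
| 0.5 | 1 − 0.975^60 | 0.781 | 1 − 0.975^30 | 0.532 |
| 0.2 | 1 − 0.99^60 | 0.453 | 1 − 0.99^30 | 0.260 |

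This measures detection within the naloxone arm and says nothing about bias in a comparison. It applies only to an event that the questioning does not reach.

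**The case against.** The strongest reply is that the document is a short summary, and one sentence does not show what the interview form contained. The symptoms are given as examples, one of them is a broad word, and asking about named symptoms is a recognised way of soliciting safety data. Much of this stands, and it rules out several stronger readings.

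- A reader might infer that only the four symptoms were asked about, or that other events were excluded. The text says neither.
- A reader might note that the drug is given under the tongue ("We randomly assigned patients to naloxone (0.4 mg/qd, sublingual) and placebo (0.4 mg/qd, sublingual") and infer that mouth reactions were not asked about. An illustrative list cannot show that.
- A reader might infer that the comparison of the arms on safety is biased. No such comparison is specified, questioning is not described as differing by arm, and equal capture leaves the expected risk ratio unchanged. What is lost is sensitivity to unexpected events and the size of absolute differences.
- A reader might take the detection probabilities as estimates for this trial. Sample size, event rate and volunteering share are all assumed.

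The reply does not remove the core of the point. Examples open the list only within the category they illustrate, and that category is presumed effects of the drug. Followed as written, the plan leaves unexpected events to be volunteered.

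It is also fair to object that the document is in the past tense and dates randomization to early 2019, so new interview questions may come too late. That changes what can be done, and the fix allows for it.

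**Conclusion.** The point holds in a limited form. The only adverse-event questioning described is framed around presumed naloxone effects, no open question or all-cause recording is described, and no safety summary is specified. Unexpected events may be under-recorded, absolute rates and risk differences for them may be understated, and any safety summary may look cleaner than it is.

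The direction rests on the sentence being a fair account of what was asked. The unchanged risk ratio rests on equal capture in the two arms, which blinding makes plausible but does not guarantee. The size cannot be derived from the documents. On the assumed 5% event rate, the chance of recording at least one event falls from 95% to between 78% and 45% with 60 on naloxone, and from 79% to between 53% and 26% with 30, as the volunteering share goes from one half to one fifth.

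This is more than a request for detail, because a better method is available at little cost. It does not threaten the primary outcome.

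**What to change.** **If interviews are still to be held, or for a follow-on trial:**

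- At each interview, ask one open question about any new or worse health problem before the symptom prompts. At Day 0 the answer provides the pre-treatment reference.
- Record every event whatever its presumed cause, with its severity and whether it was serious.
- State in the Statistical analysis section that all recorded events will be tabulated by arm.

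The cost is one question and a few form fields at interviews already scheduled, plus one table. The small downside is that more background events will be recorded in both arms.

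**If the interviews are complete:** tabulate every recorded event by arm, including any that were volunteered. State that elicitation was targeted at presumed naloxone effects, and say whether volunteered events were recorded. Do not treat the absence of unprompted events as evidence of safety. This costs one table and a few sentences.

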#### **Inclusion and exclusion criteria**

The inclusion criteria include: the participants must be above 18 years, be able to understand the study protocol and sign informed consent voluntarily, and report moderate-to-severe itch (NRS $\geq$ 3). Participants were excluded if they used anti-histamines, anti- inflammatory, anti-pruritic, analgesic, antidepressant, or anti-epileptic agents within 2 weeks prior to the study, or had a history of pruritic skin diseases such as eczema and psoriasis.

#### **Statistical analysis**

In the randomized controlled trial, an intention-to-treat (ITT) analysis was performed to evaluate the efficacy of naloxone. The last observation carry-forward (LOCF) imputation method was used for unmeasured data in drop-out participants. Mixed effect models were used to estimate the efficacy, by constructing a model:  $Y = \beta_0 + \beta_1 \text{Group} + \beta_2 \text{Time} + \beta_3(\text{Group} \times \text{Time}) + e_i + v_{ij}$ , where  $\beta_3$  is the estimate for efficacy;  $e_i$  and  $v_{ij}$  refer to the errors between individuals and within an individual (repeated measurements), respectively. Statistical analyses were performed in R Statistical Software 3.4.1. The significance level for all statistical tests was 0.05.

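### LOCF is the only stated missing-data rule; with no itch score scheduled between Day 0 and Day 7, early leavers are entered as exactly zero change, and no sensitivity analysis is stated

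*Combined protocol and SAP*

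**What the plan says.** The Statistical analysis section says that "an intention-to-treat (ITT) analysis was performed to evaluate the efficacy of naloxone" and gives one rule for missing scores: "The last observation carry-forward (LOCF) imputation method was used for unmeasured data in drop-out participants". The scores, filled in where needed, then go into a mixed model with Group, Time and their interaction. The interaction coefficient "is the estimate for efficacy". The section does not say how Time is coded or whether Day 14 contributes to that coefficient.

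The Study design section schedules the NRS face to face at baseline and on "the last day of the treatment period (Day 7"), and then by "a telephone interview on the last day of the withdrawal period (Day 14"). No score is scheduled between Day 0 and Day 7.

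The document states no other missing-data method, missingness assumption, sensitivity analysis or drop-out figure. It also does not say which value is wanted for a participant who leaves.

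**The concern.** LOCF is sometimes defended as carrying forward part of a response. That defence fails here for early leavers, because the only score available before Day 7 is the baseline. The rule therefore asserts that each of them did not change at all, and the model treats that assertion as a measurement.

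The primary outcome is exposed directly. Entry requires participants to "report moderate-to-severe itch", with a minimum score of 3, so regression to the mean or placebo response could lower the scores in both arms. If the arms then lose different fractions early, the imputed zeros remove different amounts of that shared fall and leave a between-arm difference that treatment did not cause.

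A second consequence concerns the withdrawal week. A participant lost between Day 7 and Day 14 has an on-treatment score entered as an end-of-withdrawal score.

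With one rule and nothing set beside it, a reader cannot tell how far the result depends on the rule.

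**Working it through.** **Inputs.** From the document: the three visits, the LOCF rule, the interaction coefficient as the efficacy estimate, and a 0.05 significance level (sidedness not stated; two-sided used here). The document has no sample size, SD, expected effect or drop-out figure, so there is no planned figure to reproduce.

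Everything else is assumed: 30 per arm, SD 2 at each visit, and correlation 0.5. The change SD is then √(2 × 4 × (1 − 0.5)) = 2. Early loss is varied from 5% to 20%.

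**1. Expected Day 7 estimate.** Let the mean falls be a (naloxone) and b (placebo), and the early losses dN and dP. If drop-out is unrelated to outcome, a fraction d of each arm contributes zero change. The estimate has expectation −(1 − dN)a + (1 − dP)b, where the true value is −(a − b).

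**2. Equal loss, true effect −1.50.** The effect shrinks by the drop-out fraction. Power is from 40,000 simulated change-score contrasts per case, for placebo falls of 0, 1 and 2 points:

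| Loss per arm | LOCF estimate | LOCF power | Observed-data power |
|---|---|---|---|
| 5% | 1.5 × 0.95 = 1.425, so −1.43 | 79%, 78%, 76% | 79% |
| 15% | 1.5 × 0.85 = 1.275, so −1.28 | 74%, 70%, 63% | 74–75% |

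**3. Unequal loss, no true effect.** The spurious difference is (dN − dP) × shared fall:

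| Loss, naloxone v placebo | Shared fall | LOCF estimate | Two-sided error |
|---|---|---|---|
| 10% v 5% | 2 | 0.05 × 2 = +0.10 | 5.3% |
| 15% v 5% | 2 | 0.10 × 2 = +0.20 | 6.7% |
| 20% v 5% | 2 | 0.15 × 2 = +0.30 | 9.3% |
| 5% v 20% | 2 | −0.30 | 9.4% |
| 20% v 5% | 1 | 0.15 × 1 = +0.15 | 6.1% |

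Observed data gave 4.9–5.0% throughout.

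A hand check of 20% v 5% uses the variance of a LOCF change, (1 − d) × 4 + d(1 − d) × fall². This is 3.2 + 0.64 = 3.84 in one arm and 3.8 + 0.19 = 3.99 in the other. The standard error is √(7.83/30) = 0.511, and 0.30/0.511 = 0.587. The normal approximation then gives a two-sided rejection probability of about 9.0%.

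**4. Same scenarios in a mixed model.** Random-intercept REML with Time categorical gave +0.30 and 9.3% at 20% v 5% (observed data 0.00 and 4.2%), and −0.29 and 9.7% at 5% v 20% (observed data +0.01 and 4.8%).

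**5. Day 14, if it is used.** Suppose a −1.5 effect at Day 7 is fully lost by Day 14, so the true Day 14 contrast is 0. Late loss of 5% per arm gives 0.05 × 1.5 = 0.075, so −0.075 and 5.1% error. Late loss of 20% gives 0.20 × 1.5 = 0.30, so −0.30, with error of 8.7% (change scores) or 10.7% (mixed model). Early loss of 20% v 5% with a persisting 2-point shared fall gives about +0.30 and 9%.

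**6. Drop-out related to outcome.** No true effect, 20% naloxone v 5% placebo loss, and log-odds of leaving of 0.5 per NRS point of change:

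| Who leaves more | Shared fall | LOCF | Observed data |
|---|---|---|---|
| Less relief | 2 | +0.11 | −0.20 to −0.25 |
| Less relief | 1 | −0.04 | −0.20 to −0.25 |
| Improvers | 2 | about +0.50, error 16–17% | +0.20 to +0.25 |

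For observed data, the lower value is the mixed model and the upper a comparison of completers. The less-relief and improver cases with a 2-point fall are mirror images for observed data, so the true error rate is the same in both, about 6–7%. LOCF error when people with less relief leave (2-point fall) is also about 6%.

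**The case against.** The strongest reply is that nothing shows the problem to be large. Treatment lasts one week and follow-up two, and the document supplies no drop-out figure. At 5% per arm, power is 76–79% under LOCF against 79%. At 10% v 5% loss, error is 5.1–5.3%. The striking figures need 20% v 5% loss, which nothing in the document supports. This stands, and it limits the claim.

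The second reply is that the alternative is not uniformly better. This also stands. When people with less relief leave, and more of them from naloxone, the observed-data model errs towards naloxone and lies further from zero than LOCF in both null scenarios examined. LOCF is clearly worse when improvers leave.

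Third, zero change is an error only relative to the score that would have been measured. If leavers really stay at baseline, LOCF is right for them.

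Fourth, some headline figures are change-score approximations. At 15% loss with a 2-point placebo fall, the mixed model gives 67% power, not 63%. That case also implies a 3.5-point naloxone fall on unbounded normal scores. The direction is unaffected, but the exact power should not be leaned on.

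A reader might infer differential loss from the side-effect questions ("The participants were also inquired about the possible adverse events of naloxone such as headache"). The document does not support this: asking about adverse events at each interview is not evidence that either arm lost more participants.

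**Conclusion.** The point holds as a weakness in the plan that should be fixed. That early leavers are entered with zero change follows from the visit schedule and the LOCF rule, without further assumption. The dilution and the spurious difference follow if drop-out is unrelated to outcome. The size in this trial is unknown: zero without drop-outs, near nil at low balanced loss, and about ±0.30 points with 9% two-sided error under the assumed 30 per arm, change SD of 2, 2-point shared fall and 20% v 5% loss.

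Three stronger readings are tempting and are not supported:

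- **That the trial's result is biased.** No drop-out is reported, so this cannot be said.
- **That LOCF is conservative, or that it favours naloxone.** The sign depends on which arm loses more and on who leaves. Greater placebo loss can create a false benefit, and greater naloxone loss can hide a real one.
- **That the observed-data analysis is simply correct.** It rests on missing-at-random, which cannot be tested here, and it is biased in its own way under outcome-related loss.

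**What to change.** - Fit the planned mixed model by REML to all observed NRS scores of all randomised participants, as randomised, with Time categorical so that Day 7 and Day 14 are separate contrasts.
- State what is being estimated for people who leave.
- Report drop-out by arm and visit, and by reason if reasons were recorded. If nobody dropped out, one sentence saying so settles the matter.
- Show LOCF and a delta-adjusted or placebo-based analysis as labelled sensitivity analyses. These are an essential part of the fix, since neither main method is right in every case.
- The document is written in the past tense and dates randomisation "during January 2019 to March 2019". If the data have already been analysed, label the observed-data analysis post hoc and report it beside the LOCF result.

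**Cost.** A few sentences in the plan, a refit of the same model and some additional modelling for the departure analysis. No new outcome data are needed. The price is reliance on missing-at-random. Participants with only a Day 0 score add little information on change, so the Day 7 contrast is close to a comparison of completers. If early leavers truly stay at baseline, the observed-data model overstates the effect: in the scenario above, −1.50 against −1.43 at 5% loss per arm or −1.28 at 15%.

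### Efficacy is a single Group × Time coefficient, but the Time coding, the visits modelled and the primary visit are not stated; fitted to Days 0, 7 and 14 with one Time term, it does not isolate the Day 7 on-treatment effect

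*Combined protocol and SAP*

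**What the plan says.** The Statistical analysis section states that "Mixed effect models were used to estimate the efficacy, by constructing a model". The model has an intercept, Group, Time and Group × Time, and two error terms that "refer to the errors between individuals and within an individual (repeated measurements), respectively". Of the interaction coefficient β3 it says that it "is the estimate for efficacy". The analysis is by intention to treat, and "The last observation carry-forward (LOCF) imputation method was used for unmeasured data in drop-out participants".

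The Study design section gives three assessments of the primary outcome. Day 0 and Day 7, the end of the treatment week, are face-to-face. The third is "a telephone interview on the last day of the withdrawal period (Day 14"). Nothing marks one of these visits as primary.

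The legend to the equation defines β3 and the errors but not Time. It does not say whether Time is numeric, binary or a three-level factor, or whether all three visits enter the fit.

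**The concern.** The stated aim is to learn whether blocking the receptor relieves itch. That is most naturally a question about patients on treatment, and so about Day 7, although the documents do not say this. By Day 14 patients have been off treatment for a week, so Days 7 and 14 answer different questions.

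One interaction coefficient cannot carry two separate post-baseline effects. Fitted to all three visits, it must combine them in proportions set by the coding of Time. The reported efficacy could then be on-treatment relief, off-treatment status or a mixture, and a reader of the plan cannot tell which. With numeric Time, an effect that appears only after stopping gives the same β3 as one that was present on treatment and lasted.

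**Working it through.** The plan gives no sample size, effect size or SD, so there is no figure of its own to reproduce. The check is what β3 estimates under each coding.

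**Inputs.** From the Study design section: visits at Days 0, 7 and 14. From the Statistical analysis section: the printed equation, and the two error terms, read here as a random intercept. Assumed: every participant contributes every modelled visit.

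**Step 1: visit weights.** With a random intercept and the same visits for everyone, β3 is the between-arm difference in the ordinary least-squares slope on Time. The weight on visit j is (t_j − mean t) / Σ(t − mean t)².

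- Days 0 and 7 only: centred times (−3.5, 3.5), sum of squares 24.5, weights (−1, 1)/7. Then 7 × β3 is the Day 7 difference in change.
- Numeric Time 0, 7, 14: centred (−7, 0, 7), sum of squares 98, weights (−1, 0, 1)/14. Day 7 sits at the mean time and has no weight.
- Pre/post 0, 1, 1: centred (−2/3, 1/3, 1/3), sum of squares 2/3, weights (−1, 0.5, 0.5).
- Three-level factor: two interaction coefficients, (−1, 1, 0) for Day 7 and (−1, 0, 1) for Day 14, where the plan prints one.

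The generalised least-squares weights for numeric Time were the same at within-person correlations of 0, 0.3, 0.5 and 0.8.

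**Step 2: share of the Day 7 effect returned.** Let the arms be equal at baseline, the Day 7 effect be D and the Day 14 effect be pD. Numeric Time gives 14 × β3 = pD. Pre/post gives (D + pD)/2 = D(1 + p)/2.

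**Step 3: LOCF.** Let f be the share of participants whose Day 14 score is copied from Day 7, the same in both arms and unrelated to outcome. The Day 14 difference becomes (1 − f)pD + fD, so numeric Time returns p + f(1 − p) and pre/post (1 + p + f(1 − p))/2. Both move toward 1. Neither p nor f is in the documents, so a range is shown:

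| p | numeric, f = 0 | pre/post, f = 0 | numeric, f = 20% | pre/post, f = 20% |
|---|---|---|---|---|
| −50% (rebound) | −50% | 25% | −20% | 40% |
| 0 | 0% | 50% | 20% | 60% |
| 25% | 25% | 62.5% | 40% | 70% |
| 50% | 50% | 75% | 60% | 80% |
| 75% | 75% | 87.5% | 80% | 90% |
| 100% | 100% | 100% | 100% | 100% |
| 200% (still growing) | 200% | 150% | 180% | 140% |

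The numeric estimate takes the opposite sign to the Day 7 effect when p + f(1 − p) < 0, that is p < −f/(1 − f): below 0 when f = 0, below −25% when f = 20%.

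The numeric columns use 14 × β3. With Time coded 0, 1, 2 the raw coefficient has weights (−0.5, 0, 0.5), and every numeric share is halved. The plan states no multiplier. The zero weight on Day 7 and the sign do not depend on it.

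**Step 4: check by simulation.** Assumed: 1,000 per arm, between-person SD 1.5, within-person SD 1.2, true arm differences of 0, −2 and 0 points at Days 0, 7 and 14. The numeric fit gave 7 × β3 = 0.006 (p-value 0.90), so 14 × β3 = 0.011, which is the Day 14 coefficient of the factor fit (0.011). The Day 7 coefficient of the factor fit was −2.15, and the fit to Days 0 and 7 alone also gave −2.15.

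**The case against.** The strongest reply is that the harm is conditional. The plan writes of models in the plural, so the equation may be a template fitted once per period or pair of visits; a Day 0/Day 7 fit then makes β3 exactly the Day 7 difference in change. Time may also be shorthand for a factor, in which case the Day 7 effect is estimated directly and only the naming of the primary term is missing. Both readings are open, and both limit how serious the point is. Neither is stated, and under either one there can be two efficacy coefficients with no primary one. Testing both at 0.05 would give a family-wise error of 1 − 0.95² = 0.0975 if they were independent. That figure is illustrative, because the two tests share a baseline and are correlated.

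Three further limits stand. LOCF is restricted to drop-outs, so a participant who missed Day 7 but answered on Day 14 is not clearly covered, and complete data is an assumption. The distortion can go either way: an effect still growing at Day 14 would be overstated. And the documents support no particular value of p.

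A reader might go further and infer that the efficacy result is in fact diluted, or that the contrast was picked once results were known. The documents support neither. They do not show which model was run, and an unstated contrast leaves late selection possible without being evidence of it.

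**Conclusion.** The point holds as a gap in specification with a conditional consequence. It should be fixed, but it does not rank with defects that are shown to distort the result.

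The omission is certain from the text. The algebra is exact for a three-visit fit with one Time term, a random intercept and complete data: numeric Time ignores Day 7, and pre/post coding averages it with Day 14. Either understates the Day 7 effect when p < 1 and overstates it when p > 1, on the 14 × β3 scale for numeric Time. The LOCF shares also assume equal, outcome-unrelated carry-forward in the two arms. The loss in this trial is unknown, and it is zero under a Day 0/Day 7 fit or a factor fit whose Day 7 term is the efficacy estimate.

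**What to change.** State which visits entered the model, how Time was coded and which contrast is the primary efficacy estimate.

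Preferred analysis: fit visit as a three-level factor with Group × Visit, and name the naloxone-minus-placebo difference in change from baseline at Day 7 as the single primary estimate. A primary fit to Days 0 and 7 only is an acceptable alternative. In either case, report the Day 14 difference and the Day 7-to-14 change by arm as secondary withdrawal contrasts.

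The plan is written in the past tense, so a contrast chosen after results were known should be labelled post hoc.

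Cost: the factor fit has six fixed effects instead of four (intercept, Group, two for visit, two interactions) and needs a refit of data already collected. If a Day 0/Day 7 fit is what was run, one sentence is enough. No new patients or visits are needed.

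### The efficacy coefficient β3 is not tied to a visit; with all three visits and the single Time term as written, the end-of-treatment visit (Day 7) gets zero weight

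*Combined protocol and SAP*

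**What the plan says.** Study design sets out the two phases: "The trial consisted of a one-week treatment period and a one-week withdrawal period". On timing it says "The primary outcome (severity of itch) was evaluated using the NRS through a face-to-face interview on baseline (Day 0") and again at Day 7, the last treatment day. The third assessment is "a telephone interview on the last day of the withdrawal period (Day 14"). Three measurements of the primary outcome are therefore planned, and only Day 7 is a post-baseline visit within the treatment period.

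Statistical analysis says "Mixed effect models were used to estimate the efficacy, by constructing a model". The equation has one coefficient for Group (β1), one for Time (β2) and one for their product (β3). It says that β3 "is the estimate for efficacy", and that the two error terms "refer to the errors between individuals and within an individual (repeated measurements), respectively". On missing values it says "The last observation carry-forward (LOCF) imputation method was used for unmeasured data in drop-out participants". On testing it says "The significance level for all statistical tests was 0.05".

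The documents do not say which visits enter the model, whether Time is numeric or categorical, or which between-arm contrast β3 stands for. They give no sample size, SD, within-person correlation or drop-out rate.

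**The concern.** With three visits and one interaction coefficient, β3 means different things under different readings. In a model of Days 0 and 7 it is the effect at the end of treatment. In a model of all three visits with one numeric Time term it is a slope over both weeks, one on treatment and one off it. Treatment stops at Day 7, so a benefit that fades in the withdrawal week is a plausible pattern, and the slope would not register it.

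At stake is whether the efficacy test addresses the treatment period at all. The standard error of β3 is a secondary matter. It also depends on the unstated choice.

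**Working it through.** There is no stated sample size or power figure to reproduce. The visit days, the single β3, the LOCF rule and the 0.05 level come from the documents. Every SD, correlation, mean curve and sample size below is an assumption, and tests are taken as two-sided with equal arms.

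**1. Three visits, one numeric Time term (the three-visit reading that fits the equation).** Days 0, 7 and 14 are equally spaced, and LOCF fills later gaps, so the data are balanced. Code Time 0, 1, 2, with centred values −1, 0, +1 and sum of squares 2. With a random intercept and independent within-person errors, the slope weights are −1/2, 0, +1/2. Hence

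β3 = (arm difference in Day 14 minus Day 0 change) / 2 per visit step.

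With Time in days the weights are −1/14, 0, +1/14. In one simulated data set of 80 people, β3 was 0.0042. Lowering every Day 7 value in one arm by 3 points left it at 0.0042, while its SE rose from 0.246 to 0.337.

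Let the arm difference in change be D at Day 7 and f·D at Day 14. Expected β3 is f·D/2:
- f = 1: D/2
- f = 0.5: D/4
- f = 0: 0

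Here f refers to the Day 14 values after LOCF. If a share p drops out after Day 7, unrelated to outcome and equally in both arms, and a fraction g truly remains, then f = (1 − p)g + p. With p = 20% and g = 0, f = 0.2 and β3 = 0.1·D, which comes entirely from carried-forward values.

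Effect on power: 80% power corresponds to an effect of 1.96 + 0.84 = 2.80 SEs. If the Day 14 change has the same SE and f = 0.5, the effect is 1.40 SEs and power is Φ(1.40 − 1.96) = Φ(−0.56), about 29%.

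**2. Shared curvature under the same reading.** If both arms improve by Day 7 and partly relapse by Day 14, a straight line misfits and the misfit enters the residual. With n per arm,

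residual variance = [(2n − 2)·V_lin + 2n·(V_quad + m²)] / (4n − 2), where m² = (Day 0 − 2·Day 7 + Day 14)²/6 for the shared mean.

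Take compound symmetry, SD 2, correlation 0.5 and n = 40. Then V_lin = V_quad = 4 × (1 − 0.5) = 2. The true level of a nominal 5% test is 2·[1 − Φ(1.96·√(residual variance/2))].

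| Shared change at Day 7 / Day 14 | m² | Residual variance | True level |
|---|---|---|---|
| −1 / −0.5 | 0.375 | 2.19 | 4.0% |
| −1.5 / −0.5 | 1.042 | 2.53 | 2.8% |
| −2 / −0.5 | 2.042 | 3.03 | 1.6% |
| −2 / 0 | 2.667 | 3.35 | 1.1% |

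Simulation (20,000 runs) gave 3.8%, 2.5%, 1.6% and 1.2%.

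**3. Two visits (0 and 7, or 0 and 14 in a separate model).** With two balanced visits β3 is the difference in mean change. The model SE equals the change-score SE (0.432 for both in the simulated set, Days 0 and 7), so there is no SE error. The estimate is not adjusted for Day 0. ANCOVA has variance (1 + ρ)/2 times that of the change score, multiplied by 1 + 1/(2n − 4) for estimating the slope. The effect below is set to give 80% power under a three-visit compound-symmetry model (4n − 4 df).

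| Per arm | Change score (2n − 2 df) | ANCOVA, ρ = 0.5 | ANCOVA, ρ = 0.7 |
|---|---|---|---|
| 40 | 79.5% | 89.1% | 85.1% |
| 20 | 79.0% | 88.2% | 84.0% |
| 10 | 77.7% | 86.0% | 81.5% |

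**4. Secondary: three visits, categorical Time, random intercept only.** This needs two interaction coefficients, not the one written. For complete data, model SE / true SE = √(mean of the three pairwise difference variances / variance of the tested difference). With SD 2 and correlations (0–7, 0–14, 7–14) of 0.5/0.4/0.6, the difference variances are 4.0, 4.8 and 3.2, with mean 4.0. The ratio is 1.00 for Day 7 (level 5.0%) and 0.913 for Day 14 (7.4%). With 0.4/0.6/0.4 the levels are 6.5% and 2.4%. The direction depends on correlations that the documents do not give.

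**The case against.** The strongest reply is that the authors may have fitted separate two-visit models. The section speaks of models in the plural, and one β3 fits a binary Time term. On that reading Day 7 gets full weight and the SE is sound. This stands as a possibility. It does not remove the point, because the text does not say so and would then contain two efficacy coefficients without naming the one that counts.

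A reader might go further and infer that the test is anti-conservative, with a true level of 8% to 10%. The documents do not support that. Most such figures arise under categorical Time, which does not match the equation. Compound symmetry is itself inferred: no structure is named for the within-person error and none is excluded. No variances or correlations are given. Under numeric Time, the assumed curves in the second step make the test conservative. A level of 8.4% appears there only with an assumed decaying correlation (0.5/0.25/0.5) and flat means. With the same correlations and a shared curve of −2/−0.5 it is 3.8%.

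A reader might also infer that the trial did ignore Day 7, or that Day 7 is the declared primary time point. Neither is stated.

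Finally, the document is in the past tense, so choosing Day 7 now could be a post hoc choice of contrast. That objection stands and is met in the fix.

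**Conclusion.** The point holds in a limited form and should be addressed. The plan does not link its efficacy coefficient to a visit. Followed literally with all three visits, β3 is half the Day 14 contrast, and an on-treatment benefit that is gone by Day 14 has expected β3 of zero. This is algebra for balanced data with a random intercept and does not depend on any assumed SD. The power drop to about 29% at f = 0.5 and the true levels of about 4% down to 1% do rest on the stated assumptions.

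If two visits were meant, the SE is right, and the remaining weakness is efficiency. At an assumed correlation of 0.5, ANCOVA adds 8.3 to 9.6 points of power (86.0 − 77.7 at 10 per arm; 89.1 − 79.5 at 40). The covariance point survives only conditionally, for categorical Time with a random intercept alone. Its size and direction are unknown.

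**What to change.** State in Statistical analysis that the efficacy estimate is the between-arm contrast at Day 7. Estimate it by ANCOVA of Day 7 NRS on Day 0 NRS, and report Day 14 as a separate analysis.

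If all visits are to be modelled jointly, use categorical Time with an unstructured within-person covariance and Kenward-Roger or Satterthwaite degrees of freedom, and report the Day 7 and Day 14 contrasts separately.

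The cost is a change of wording and code, with no new data. ANCOVA requires the extra Day 14 analysis. If compound symmetry is in fact true, the unstructured model loses 0.5 points of power at an assumed 40 per arm (80% to 79.5%), 1.0 at 20 and 2.3 at 10 (80% to 77.7%). In simulations with 20% LOCF under several assumed covariances, true levels were 4.7–5.2% for the unstructured model and 4.6–5.2% for ANCOVA. Neither option removes any bias from LOCF, which is a separate matter.

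If the data have already been analysed, label the change as post hoc and report it beside the model as written, stating which visits and Time coding that model used.
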